1. INTRODUCTION

The purpose of this reporting and analysis plan (RAP) is to describe the analyses to be included in the Synoptic Clinical Study Report for Protocol of study 205864 (GSK Document No 2016N293064_3)

Revision Chronology:		
2016N293064	21-MAR-2017	Original
2016N293064_01	17-MAY2017	Excludes the enrolment of women of childbearing potential
2016N293064_02	24-JUL-2017	Removal of requirement for male contraception with partners of WOCBP. Addition of mobile spirometer (MicroDiary) as a medical device
2016N293064_03	18-MAY-2018	Updated to reflect that cohorts in addition to COPDGene may be used to support recruitment. Removed the use of the Random Forest data in patient selection and changed history of lung function decline from 20mL/yr to 15 mL/yr. Changed inclusion criteria from weight >45kg to body mass index ≥ 21 .

2. SUMMARY OF KEY PROTOCOL INFORMATION

2.1. Changes to the Protocol Defined Statistical Analysis Plan

Changes from the originally planned statistical analysis specified in the protocol are outlined in [Table 1](#).

Table 1 Changes to Protocol Defined Analysis Plan

Protocol	Reporting & Analysis Plan	
Statistical Analysis Plan	Statistical Analysis Plan	Rationale for Changes

 All Participants population 	
 All Subjects population 	
 R&D Clinical Data Standards Board (CDSB) recommendation to use the term 'Subjects' in all displays (Tables, Figures & Listings)

 Random coefficients model analysis of rate of decline in FEV₁ 	
 Summary Statistics 	
 Early study termination

 MMRM analysis of change from baseline of SGRQ-C and SGRQ-C domains 	
 Summary Statistics 	
 Early study termination

 SGRQ Responder analysis 	
 No analysis 	
 Early study termination

 Time to first HCRU COPD exacerbation 	
 No analysis 	
 Early study termination

 Study Population and Efficacy deliverables on ITT Population 	
 Change population of Study Population and Efficacy deliverables from ITT to 	
 Consistency among danirixin project

Protocol	Reporting & Analysis Plan	
Statistical Analysis Plan	Statistical Analysis Plan	Rationale for Changes
	Safety population	
 Primary interest on safety results Study Population and Efficacy tables should be a reflection of the focus

 Per protocol population 	
 Removal of per protocol population 	
 No analysis using per protocol population

2.2. Study Objectives and Endpoints

Objectives	Endpoints
Primary Objectives	Primary Endpoints

 To assess whether danirixin HBr 35mg tablets impact disease progression compared with placebo 	
 Rate of decline in FEV₁ (post-bronchodilator) Change from baseline in St. George's Respiratory Questionnaire (SGRQ) total score (derived from SGRQ-C) at the end of the 52-week treatment period
Secondary Objectives	Secondary Endpoints

 To further characterize the safety of danirixin HBr 35mg compared to placebo in participants with mild to moderate airflow limitation 	
 Adverse events Vital Signs Electrocardiogram (ECG) Clinical Laboratory Assessments (haematology, clinical chemistry, urinalysis, and/or other safety biomarkers)

 To further characterize the clinical activity of danirixin HBr 35mg tablets compared with placebo 	
 Time to first HCRU COPD exacerbation Change from baseline in FEV₁ (post-bronchodilator) SGRQ responder analysis SGRQ domains COPD Assessment Test (CAT) Rescue medication use

2.3. Study Design

Overview of Study Design and Key Features	
<pre> graph LR A[Screening¹] -- 32 days --> B((R)) B --> C[Placebo (n=50)] B --> D[Danirixin, 35mg (n=50)] C -- 52 weeks --> E[Follow-up²] D -- 52 weeks --> E </pre> 
¹ If changes to medication are required, consent must be signed prior to any changes being made and may occur prior to the Screening Visit
 
² Follow-up visit to occur within 28 days of last dose of study medication
	
Design Features	
 This study will be conducted as a multi-centre, randomized, double-blind, sponsor open, placebo-controlled, 52-week study investigating the potential impact of danirixin HBr 35mg tablets compared with placebo on disease progression in participants with mild to moderate airflow obstruction. Participants will be randomized 1:1 to either danirixin HBr 35mg or placebo. The randomization will be stratified based on smoking status (current or former smokers).
Dosing	
 Study treatment will be administered twice daily for 52 weeks.
Time & Events	
 Refer to Appendix 2: Schedule of Activities
Treatment Assignment	
 Participants will be randomized (1:1) to receive either danirixin HBr 35mg or placebo. Participants will be instructed to take one tablet twice daily with food GSK RandAll NG used to generate randomization schedules. Randomization will be stratified based on smoking status (former vs. current)
Interim Analysis	
 No interim analysis is planned for the study.

2.4. Statistical Analyses

Due to the early termination of the study, the primary efficacy endpoint cannot be met and no formal analysis will be done with the small number of participants contributing minimal data. The core safety summaries and available summary statistics for primary and secondary endpoints will be presented.

3. PLANNED ANALYSES

3.1. Final Analyses

The final planned primary analyses will be performed after the completion of the following sequential steps:

1. All participants have completed the final (early withdrawal) visit, are deemed lost to follow-up or are deceased.
2. All required database cleaning activities have been completed and final database release (DBR) has been declared by Data Management.
3. All criteria for unblinding the randomization codes have been met.
4. Randomization codes have been distributed according to RandAll NG procedures and study is unblinded.
5. Database freeze (DBF) is declared by Data Management.

4. ANALYSIS POPULATIONS

Population	Definition / Criteria	Analyses Evaluated
All Subjects	
 All participants who were screened for eligibility and for whom a record exists on the study database and will be used for the tabulation, listing of reasons for withdrawal before randomization and listings of AEs and SAEs for nonrandomized participants. 	
 Subject Disposition Reasons for withdrawal before randomization. Inclusion, exclusion, and randomization criteria deviations
Safety	
 This population will comprise all participants randomized to treatment, excluding those who were randomized in error (participants randomized in error will be recorded as screen failures), who take at least one dose of study treatment. Participants will be analysed according to the treatment they actually received. This will constitute the primary population for all analyses and summaries of efficacy and safety. Outcomes will be reported according to the actual treatment allocation. 	
 Safety Primary analysis Study Population Efficacy Health-related Quality of Life Assessments Inhaler Assessments

NOTES: Please refer to [Appendix 10: List of Data Displays](#) which details the population to be used for each display being generated.

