6. STUDY POPULATION ANALYSES

6.1. Overview of Planned Study Population Analyses

The study population analyses will be based on the Safety Population, unless otherwise specified.

Study population analyses including analyses of participants' disposition, protocol deviations, medical history, demographic and baseline characteristics, prior and concomitant medications, and exposure will be based on GSK Core Data Standards. Details of the planned displays are presented in [Appendix 10: List of Data Displays](#).

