7.1.3. Population of Interest

The primary efficacy analyses will be based on the Safety population, unless otherwise specified.

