7.2.3. Population of Interest

The summary of secondary endpoints will be based on the Safety population, unless otherwise specified.

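### SAP Section 4 promises AE and SAE listings for nonrandomized participants that Appendix 10 lacks, and its Safety definition as worded would drop anyone randomized in error who was dosed

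*SAP*

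**What the plan says.** Section 4 of the SAP defines two populations.

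- **All Subjects** is everyone screened who has a record on the database. Among its stated uses are "listings of AEs and SAEs for nonrandomized participants".
- **Safety** is the randomized participants, "excluding those who were randomized in error (participants randomized in error will be recorded as screen failures), who take at least one dose". They are analysed by the treatment actually received. It is the main population for both efficacy and safety.

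The note under the table sends the reader to Appendix 10, which "details the population to be used for each display being generated".

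Table 1 in Section 2.1 moves the study population and efficacy displays from ITT to Safety and gives as one reason "Primary interest on safety results". Section 2.4 limits the report to description: "The core safety summaries and available summary statistics for primary and secondary endpoints will be presented". Sections 6.1, 7.1.3, 7.2.3 and 8 all name Safety as the default population.

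**The concern.** There are two separate problems, and both concern who appears in the adverse event reporting.

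1. **A promised output is missing from the display list.** Programmers work from Appendix 10. If they follow it, an AE or SAE in a participant who was never randomized appears in no output, although Section 4 says it will be listed. Such events are plausible: screening can last up to 32 days, and consent may be signed before medication changes that precede the Screening Visit (Sections 2.3 and 10.2.1).
2. **The Safety definition carries two conditions that do not fit together.** It requires a dose, and it also removes anyone randomized in error. Read literally, a participant randomized in error who took study treatment leaves Safety and is recorded as a screen failure. That person's events would then be missing from every adverse event display.

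The report has no formal efficacy analysis, so complete accounting of adverse events is a large part of what it delivers.

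**Working it through.** The SAP states no figure to reproduce. The check compares Section 4 with the population column of Appendix 10 (Sections 10.10.3 to 10.10.7) and then takes the Safety clause case by case.

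**Step 1: which displays use All Subjects**

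| Display | Content | Shows AEs? |
|---|---|---|
| Table 1.2 | Screening status, screen failure reasons | No |
| Table 1.6 | Eligibility deviations among screen failures | No |
| Table 1.8 | Study populations | No |
| Listing 1 | Screen failure reasons | No |
| Listing 7 | Eligibility deviations of screen failures | No |
| Listing 9 | Subjects left out of a population | No |

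Three tables + three listings = 6 displays, of which 0 show adverse events.

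**Step 2: which population the adverse event displays use**

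- Tables 3.1 to 3.9: 9, all Safety.
- Figure 3.1: 1, Safety.
- Listings 15 to 22: 8, all Safety.

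9 + 1 + 8 = 18, all on Safety. Listing 23 (treatment details) stands under the same SAE heading. It is not counted because it does not list events, and it too is on Safety.

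**Step 3: whether anything else fills the gap**

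- Table 3.6 covers pre-treatment SAEs but is on Safety, so it reaches only participants who were later dosed.
- Section 8 lets displays depart from Safety where this is specified, but Appendix 10 specifies no departure for any adverse event display.
- Table 1 in Section 2.1 does not record the listing as dropped. Its All Participants row records only a change of name.
- Section 10.10.1 closes the listings at 37, so no unnumbered listing is implied.

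**Step 4: the randomized-in-error clause**

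| Randomized in error and... | Effect of the dose condition | Effect of the exclusion clause |
|---|---|---|
| took no dose | Already outside Safety | None: redundant |
| took a dose | Would be in Safety | Removed and recorded as a screen failure |

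No third case exists. In the second, the participant would count in the screen-failure figures of Table 1.2 and in the denominator of Table 1.6. Exposure (Table 1.24, Listing 14), planned and actual treatment (Listing 5) and all 18 adverse event displays would omit that person. Listing 9 would still show the exclusion.

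The SAP does not define the term. Table 1.7 and Listing 8 report eligibility deviations within Safety, so ineligibility alone evidently does not remove a dosed participant. The SAP gives no rule for telling the two groups apart.

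**Step 5: how the two parts combine**

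The listing promised in Section 4 is for nonrandomized participants. By that wording it would not cover a participant who was randomized and dosed in error, nor one who was randomized and never dosed.

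**The case against.** The absence of the listing cannot be disputed, but several points limit its weight.

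- **The conflict is one phrase.** The column of analyses for All Subjects in Section 4 names disposition, withdrawal before randomization and eligibility deviations, not adverse events, and so agrees with Appendix 10. Deleting the phrase would also remove the contradiction. That is true, but it would leave the events unreported, and Table 1 records no decision to drop them.
- **The exclusion may be meant only for the undosed.** Recording someone as a screen failure fits a person who never started treatment, and the protocol, not shown here, may define the term that way. This stands: the second part is conditional. The SAP wording itself does not contain the limit.
- **An exclusion would be visible.** Listing 9 would show it. This stands too, but the listing would not show the person's events.

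A reader might also infer more than the documents support:

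- *That exposed participants have been, or will be, hidden.* The SAP does not say that anyone was dosed after randomization in error.
- *That the dominance of Safety in Appendix 10 measures the defect.* It does not. Safety is the declared main population; the discrepancy is one missing kind of listing and one clause.
- *That a comparison between arms is distorted.* Nonrandomized participants have no arm, no formal analysis is planned, and no between-arm result is shown to change.

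**Conclusion.** The point holds in two parts of different strength.

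The first is certain from the text. Section 4 promises AE and SAE listings for nonrandomized participants and Appendix 10 provides none: 18 of 18 adverse event displays are on Safety, and 0 of 6 All Subjects displays show adverse events.

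The second is a drafting fault whose effect is conditional. As worded, the Safety definition removes a participant randomized in error even if dosed. It matters only if such a participant exists; otherwise the clause does nothing.

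Neither the number of nonrandomized participants with an event nor the number dosed after randomization in error is given, and either may be zero. The consequence is possible incompleteness of safety reporting. It is worth correcting because the repair is small and needs no new data.

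**What to change.** 1. Add to Appendix 10 one All Subjects listing of AEs and SAEs, with seriousness flagged, for participants not in Safety. Change the listing range in Section 10.10.1 from 1 to 37 to 1 to 38 (37 + 1). Defining the listing as everyone outside Safety goes slightly beyond the Section 4 promise, but it also covers participants randomized and never dosed.
2. In Section 4, either delete the randomized-in-error exclusion or state that it applies only to participants who took no dose. Either way, every dosed randomized participant is then in Safety by treatment received, and none is counted as a screen failure.

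**Cost:** SAP wording, one additional listing and a check of one population flag. Any dosed participant randomized in error would enter the Safety denominators. These also serve the study population and efficacy summaries, because Sections 6.1, 7.1.3 and 7.2.3 use the same population.

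### Efficacy tables are grouped by treatment received, without a reason that applies to efficacy; group them by randomised treatment within the same dosed population

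*SAP*

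**What the plan says.** SAP Table 1 (Section 2.1) gives the protocol's plan as "Study Population and Efficacy deliverables on ITT Population" and the new plan as "Change population of Study Population and Efficacy deliverables from ITT to" the Safety population. The reasons listed are consistency across the danirixin project, "Primary interest on safety results", and the wish that the study population and efficacy tables reflect that focus.

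Section 4 defines the Safety population as randomised participants who took at least one dose, "excluding those who were randomized in error (participants randomized in error will be recorded as screen failures". It then sets the grouping: "Participants will be analysed according to the treatment they actually received", restated as "Outcomes will be reported according to the actual treatment allocation". On scope it says: "This will constitute the primary population for all analyses and summaries of efficacy and safety".

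Section 7.1.3 applies this to the primary endpoints: "The primary efficacy analyses will be based on the Safety population, unless otherwise specified". Section 7.2.3 does the same for the secondary endpoints. Appendix 10 assigns the Safety population to every efficacy table (2.1 to 2.15) and to the demographic and baseline characteristics tables (1.9 to 1.15). Section 4 keeps only two populations, All Subjects and Safety, and no efficacy display by randomised treatment remains.

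Section 2.4 states that early termination rules out a formal efficacy analysis. Sections 7.1.5 and 7.2.4 limit efficacy to descriptive statistics.

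**The concern.** Two choices are bundled into the change: who is included, and which column they appear in. The reasons in Table 1 bear on the first. A terminated study whose interest is now safety can reasonably be reported on one set of dosed participants. None of those reasons explains why lung function, SGRQ, CAT and rescue use should be sorted by the tablet taken and not by the arm assigned. Sorting by treatment received is the usual convention for safety, where the question is what exposure was followed by which event. For efficacy, the reason to compare two columns is that randomisation formed them.

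The efficacy tables will still be read as a comparison. Section 2.2 frames the primary objective as danirixin against placebo, Section 2.3 describes 1:1 randomisation stratified by smoking status, and Section 5.1 fixes a danirixin versus placebo display. A reader will take the two columns to be the randomised arms. Under the Section 4 rule they are not defined that way, and any participant classified under the other treatment would change columns without the efficacy tables showing it.

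The rule is also less definite than it looks. The SAP does not say how to classify a participant who received both treatments at different times during the planned 52 weeks. Randomised assignment has no such ambiguity.

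**Working it through.** The SAP states no figure on this point, so there is none to reproduce. The check has two parts.

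**1. When do the two groupings differ?**

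- Everyone in the Safety population was randomised and dosed (Section 4).
- Among these participants, grouping by treatment received and grouping by randomised treatment differ only for those classified under a treatment other than the one assigned.
- Let k be the number of such participants. The SAP does not give k. If k = 0, the two groupings are identical and every efficacy table is the same either way.
- Membership relative to ITT is a separate question. Participants never dosed, or randomised in error, are outside the Safety population. How many of them ITT would have kept cannot be judged, because this SAP does not define ITT.

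**2. How much could one case matter?**

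This is an illustration with the following inputs.

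- n per arm: 50 is the planned size (Section 2.3). 10 is an assumption, standing for the small number that Section 2.4 mentions without a figure.
- k = 1, assumed.
- d = 1 to 2, assumed: the distance of that participant's value from the arm mean, in SD units.
- No true difference, a common SD, and both as-randomised means set to 0.

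Suppose k participants randomised to placebo, each at +d, are moved to danirixin. The remaining placebo mean becomes −kd/(n − k), and the danirixin mean becomes kd/(n + k). The displayed difference therefore moves by

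shift = kd/(n + k) + kd/(n − k).

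The standard error of a difference between two arms of n is √(2/n) in SD units.

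| n per arm | Share of arm moved | Shift, d = 1 | Shift, d = 2 | Standard error |
|---|---|---|---|---|
| 50 (planned) | 1/50 = 2% | 1/51 + 1/49 = 0.04 SD | 2/51 + 2/49 = 0.08 SD | √(2/50) = 0.20 SD |
| 10 (assumed) | 1/10 = 10% | 1/11 + 1/9 = 0.20 SD | 2/11 + 2/9 = 0.40 SD | √(2/10) = 0.45 SD |

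In every case the shift is smaller than the standard error. It comes close only for the most extreme case shown (n = 10, d = 2). The shift is proportional to d, so a participant near the arm mean moves almost nothing.

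**The case against.** The strongest reply is that little depends on this. The change is openly declared in Table 1 with reasons. No efficacy model, test or estimate of a treatment difference is planned; the tables give summary statistics by arm for a study that stopped early. Any participant on the wrong treatment would appear in Listing 5 (planned and actual treatments). Even the illustrated shifts are below the sampling error. Keeping two groupings for descriptive tables could be called a matter of taste.

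Most of this stands, and it limits the weight of the point. It does not supply a reason for the grouping. Listing 5 would reveal a wrong-treatment case but would not put that participant back in the randomised column.

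Three stronger readings are tempting, and the document does not support them.

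- A reader might infer that the efficacy summaries no longer compare the randomised groups at all. Everyone in the Safety population was randomised, and among dosed participants the columns change only if k is above zero. The SAP reports no such case.
- A reader might take Listing 5 as a sign that the sponsor expects mis-allocation. It carries a standard shell (TA1) with the note IDSL, the sponsor's standards library. It is a routine safeguard and says nothing about how many cases there are.
- A reader might conclude that the ITT set must be restored. Its definition is not in this SAP, so its membership and its effect on the tables cannot be checked. Confining the Safety population to the safety displays would also leave other study population tables, such as disposition (1.1), treatment status (1.3), important deviations (1.5) and exposure (1.24), without an assigned population.

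**Conclusion.** The point holds in a limited form. Section 4 applies grouping by treatment received to efficacy, Table 1 gives no reason that bears on that grouping, and no display by randomised treatment is kept. The efficacy columns would depart from the randomised arms if anyone was classified under the wrong treatment, and only then among dosed participants.

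The size is unknown, because the count is not given and may be zero. With one case and the assumed values above, the displayed difference moves by 0.04 to 0.08 SD at the planned arm size and by 0.20 to 0.40 SD at an assumed 10 per arm, less than the standard error in both settings. Since efficacy is descriptive only, no test result or formal conclusion is at risk. The point is worth acting on because the correction needs no new data and leaves the tables unchanged if there were no such cases.

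**What to change.** In SAP Section 4, separate membership from grouping. Keep the Safety population as the set of dosed participants. State that the efficacy tables (2.1 to 2.15) and the demographic and baseline characteristics tables (1.9 to 1.15) are grouped by randomised treatment within that set, and that the safety displays are grouped by treatment received. Limit the two sentences on actual treatment to the safety displays, and let Sections 7.1.3 and 7.2.3 refer to the revised text.

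If planned and actual treatment agree for every participant, say so in the report; the tables are then the same under either rule.

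The cost is a few lines of SAP text and the planned-treatment variable in place of the actual-treatment variable in the affected tables. No new data and no new population are needed. Returning to the protocol's ITT set is optional and depends on its definition, which this SAP does not give.
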